## 8.3. Variables

For a detailed list of variables of interest and availability by registry, see Annex 3 – Table 5.

## 8.3.1. Patient Baseline Characteristics

Baseline variables are collected at the index date. These variables reflect the patient's demographics and status at the initiation of filgotinib treatment including relevant medical history at or prior to the index date. Baseline variables will include (as per availability by each registry):

- Age (at baseline)
- Sex
- Body mass index (BMI)
- Long-time smoking (for >10 years (Kristensen et al., 2023) (either current or past smoking)
- Date of UC diagnosis

- Severity of UC (for details, see Annex 3 Table 5)
- Renal impairment (for details, see Annex 3 Table 5)
- Hepatic impairment
- Type and number of previous UC treatments prior to filgotinib initiation
- Date of filgotinib initiation
- Initial filgotinib dose
- Diagnosis of active TB at index date
  - Date of diagnosis
- Active serious infection at index date
  - Date of diagnosis
- Current pregnancy (at index date)
  - Start of pregnancy
- Age  $\geq 65$  (at index date)
- History of atherosclerotic CVD (angina, coronary heart disease, myocardial infarction, congestive heart failure, stroke, peripheral arterial disease)
- Other CV risk factors (diabetes mellitus, hypertension, obesity/BMI  $\geq$  30 kg/m^2)
- Current malignancy
- History of malignancy
- Concomitant use of other immunosuppressants
- Diagnosis of viral hepatitis
  - Date of diagnosis
- Diagnosis of herpes zoster
  - Date of diagnosis
- Screening for viral hepatitis
  - Date of screening
- Laboratory measurements (measurement within ±1 month of filgotinib index date, or any time during follow-up)
  - absolute neutrophil count (ANC)
  - absolute lymphocyte count (ALC)
  - hemoglobin (Hb)
- Use of live-attenuated vaccines
- History of VTE
- Recent surgery (i.e. surgery within 1 month (Singh et al., 2023) prior to the index date or at any time during follow-up; see also Annex 3 Table 5)
- Reduced mobility (for details, see Annex 3 Table 5)
- Recent hospitalization (hospitalization within 1 month prior to the index date or at any time during follow-up; see also Annex 3 Table 5)
- History of blood clotting disorders
- Concomitant use of combined hormonal contraceptives
- Concomitant use of hormone replacement therapy

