# 7. RESEARCH QUESTION AND OBJECTIVES

Information on prescribing of filgotinib for UC under real-world clinical practice is scarce, specifically, in the context of the updated prescribing information and HCP Guide after implementation of Article 20 decisions on JAKi's.

Therefore, this longitudinal DUS aims to describe physicians' adherence to the prescribing information of filgotinib in real-world clinical practice and to evaluate the effectiveness of the aRMMs by assessing how HCPs prescribing filgotinib adhere to the information provided in the SmPC in conjunction with the information in the HCP Guide with a specific focus on aRMMs implemented after the EC Article 20 decision on JAKi's (i.e. after 10 March 2023).

The objectives of this study are as follows:

- a. To describe the characteristics of patients treated with filgotinib in terms of:
- Demographics (e.g., age and sex)
- Comorbidities and prior and current medication use
- b. To evaluate prescribers' adherence to the filgotinib aRMMs, specifically:
- Compliance with the recommended posology (average daily dose) and duration of use
- Compliance with recommendations for patient screening and laboratory monitoring prior to and during treatment
- Compliance to recommendations for use in patients with moderate to severe chronic renal impairment/end stage renal disease or severe hepatic impairment
- Compliance with recommendations for limitations of use, including:
  - Use in patients with risk factors for venous thromboembolism (VTE)
  - Use in patients aged 65 years and older
  - Use in patients with risk factors for cardiovascular (CV) disease
  - Use in patients with risk factors for malignancy

- Use in patients with risk factors for serious infections
- Use in patients with concomitant use of other potent immunosuppressants
- Use of live attenuated vaccines
- Contraindicated use
- Compliance with discontinuation of filgotinib treatment in patients experiencing VTE

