## **Annex 3 Additional Information**

#### Variables of Interest

#### Table 5Variables of Interest and Their Availability by Registry

Variable	Availability in individual registries yes/no (additional comments)					
	ENEIDA (ES)	ICC (NL)	SWIBREG (SE)			
Variables assessed at baseline (start [index] date of filgotinib)						
Key patient characteristics						
Age: Date/year of birth	yes	yes	yes (Population Register)			
Sex	yes	yes	yes (Population Register)			
BMI	no (might be in medical report)	yes	yes (SWIBREG, but suboptimal coverage)			
Height	yes (not always available; might be in medical report)	yes	yes (SWIBREG, but suboptimal coverage)			
Weight	no (might be in medical report)	yes	yes (SWIBREG, but suboptimal coverage)			
Dx of UC	yes	yes	yes			
Date/year of Dx	yes	yes	yes			
Renal impairment (moderate to severe chronic kidney disease [stage 4 or 5])	yes (not always available; might be in medical report [and as described in the medical history of the patient])	yes (creatinine lab values are available)	yes (NPR via ICD10- and NCSP codes) (ICD10-codes: N17 - Acute renal failure N183 - Chronic kidney disease, stage 3 N184 - Chronic kidney disease, stage 4			

Variable	Availability in individual registries ves/no			
		(additional comments)		
	ENEIDA (ES)	ICC (NL)	SWIBREG (SE)	
	ENEIDA (ES)		SWIBREG (SE) N185 - Chronic kidney disease, stage 5 N189 - Chronic kidney disease, unspecified N19 - Unspecified kidney failure Y841- Kidney dialysis Z992 - Dependence on renal dialysis) NCSP-codes: DK001 - Installation of tunnelled hemodialysis catheter DK005 - Tunneled hemodialysis catheter replacement DR014 - Hemodiafiltration DR015 - Hemodialyis, acute DR016 - Hemodialyis, chronic DR020 - Continuous arteriovenous or venovenous hemofiltration DR025 - Preoperative hemodilution DR056 - Heparin-free dialysis DR060 - Home hemodialysis control DR061 - Home hemodialysis	
Severe hepatic impairment (Child Pugh C)	yes (not always available; might be in medical report)	yes	start yes (NPR via ICD-codes)	

Variable	Availability in individual registries yes/no (additional comments)			
	ENEIDA (ES)	ICC (NL)	SWIBREG (SE)	
UC treatment prior to initiation of filgotinib (specifically other JAKi's; advanced therapies; immunomodulators/immunosuppressants)	yes	yes	yes	
JAKi's	yes	yes	yes	
Advanced therapies – biologics (including TNFα inhibitors)	yes	yes	yes	
Advanced therapies – non-biologics	yes	yes	yes	

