Myocardial infarction	no (might be in medical report)	yes (as part of medical history/comorbidity)	yes (NPR)
Congestive heart failure	no (might be in medical report)	yes (as part of medical history/comorbidity)	yes (NPR)
Stroke	no (might be in medical report)	yes (as part of medical history/comorbidity)	yes (NPR)
Peripheral artery disease	no (might be in medical report)	yes (as part of medical history/comorbidity)	yes (NPR)
Other CV risk factors		yes (as part of medical history/comorbidity)	yes (NPR)
Diabetes mellitus (type 1 or 2)	yes (if not available, might be in medical report)	yes (as part of medical history/comorbidity)	yes (NPR)
Hypertension	yes (if not available, might be in medical report)	yes (as part of medical history/comorbidity)	yes (NPR)
Obesity/BMI	no (might be in medical report)	yes (as part of medical history/comorbidity)	yes (NPR)
Current malignancy	yes (if not available, might be in medical report)	yes (as part of medical history/comorbidity)	yes (Cancer Register)
Hx of malignancy	yes (if not available, might be in medical report)	yes (as part of medical history/comorbidity)	yes (Cancer Register)

Variable	Availability in individual registries yes/no (additional comments)		
	ENEIDA (ES)	ICC (NL)	SWIBREG (SE)
Previous VTE	yes (if not available, might be in medical report)	yes (as part of medical history/comorbidity)	yes (NPR)
Recent surgery (within 1 month prior to the index date or at any time during follow-up)	no (might be in medical report if related to IBD surgery)	yes (as part of medical history/comorbidity; history and location of IBD surgery is collected, and any IBD- surgery during follow-up)	yes (NPR)
Date of surgery	only IBD-related surgery; others might be in medical report	yes	yes (NPR)
Reduced mobility	no (might be in medical report)	no	yes (immobilization cannot be reliably captured in the Swedish registers; inpatient care due to UC [i.e., UC as main diagnostic listing] which will capture hospitalized patients in NPR; by proxies, e.g. major orthopedic surgery [pelvis/abdomen, hip or knee replacement; knee arthroscopy]; any surgery that requires immobilization post- procedure including fracture surgery and amputation of lower limbs; some types of vascular and orthopedic surgery)
Recent hospitalization (within 1 month prior to the index date or at any time during follow-up)	no (might be in medical report)	yes (hospitalizations are registered during follow-up)	yes (hospitalization record in the inpatient part of the NPR;

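### Three baseline items in Section 8.3.1 have windows open to all of follow-up, so post-index operations, admissions and blood tests can count as baseline

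*Protocol*

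**What the plan says.** Section 8.3.1 opens with a clear rule: "Baseline variables are collected at the index date". They are to reflect the patient's "status at the initiation of filgotinib treatment including relevant medical history at or prior to the index date". Three entries in the list that follows do not keep to it:

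- ANC, ALC and haemoglobin: "Laboratory measurements (measurement within ±1 month of filgotinib index date, or any time during follow-up".
- Hospitalization: "Recent hospitalization (hospitalization within 1 month prior to the index date or at any time during follow-up".
- Surgery: the same structure, one month before the index date or any point in follow-up.

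Annex 3, Table 5 places surgery ("Recent surgery (within 1 month prior to the index date or at any time during follow-up") and hospitalization in the block headed "Variables assessed at baseline (start [index] date of filgotinib", within the rows on VTE. For hospitalization, the ICC cell reads "yes (hospitalizations are registered during follow-up".

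Section 8.3.2 lists ANC, ALC and haemoglobin again as follow-up variables. It has no entry for surgery or hospitalization, and neither does the follow-up part of Table 5. Objective b in Section 7 includes "Compliance with recommendations for patient screening and laboratory monitoring prior to and during treatment".

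**The concern.** A baseline risk factor in this study is meant to show what the prescriber faced when starting filgotinib. An admission or operation after that date could not have informed the decision. If it is counted, the share of patients apparently treated despite a VTE risk factor is inflated. The inflation grows with time observed, so a registry with longer treatment, or the 4-year final report against the 2-year interim report, shows a higher baseline figure with no change in prescribing.

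For laboratory tests the issue is the split between testing before and during treatment, which objective b needs. A baseline item that also accepts on-treatment tests blurs that split.

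**Working it through.** **The plan's own figure.** The protocol gives no rate for these items. Its only related figure is the precision example in Section 8.5: a high-risk proportion of 10% with n = 300. SE = √(0.10 × 0.90 / 300) = 1.73%, and 10% ± 1.96 × 1.73% gives 6.6% to 13.4%. This reproduces and is not in dispute.

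**The windows side by side.**

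| Item | Baseline window, 8.3.1 | Own follow-up entry in 8.3.2? |
|---|---|---|
| ANC, ALC, Hb | ±1 month, or any time in follow-up | Yes |
| Recent surgery | 1 month before, or any time in follow-up | No |
| Recent hospitalization | 1 month before, or any time in follow-up | No |

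For laboratory tests, the follow-up clause duplicates an item that already exists. For surgery and hospitalization, the baseline entry is the only definition, so pre-index and post-index events share one variable.

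**ICC.** Section 8.4.2.4.1 (Week 0) does not list hospitalization among the data collected. Section 8.4.2.4.2 (follow-up visits) does. With the Table 5 cell quoted above, the ICC baseline value would come largely or wholly from events after the index date.

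**SWIBREG.** Table 5 takes hospitalization from inpatient records in the National Patient Register, and VTE events from the same register. As written, an inpatient admission for a VTE on treatment would meet that patient's own baseline risk-factor item.

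**Illustrative size.** Assume a constant rate r of 0.10 to 0.20 hospitalizations per patient-year, the same before and after the index date. The proportion with at least one event in time t is 1 − exp(−r × t).

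| Window | r = 0.10 | r = 0.20 |
|---|---|---|
| 1-month look-back (t = 1/12) | 0.8% | 1.7% |
| 1 full year of follow-up (t = 1) | 9.5% | 18.1% |
| 2 full years of follow-up (t = 2) | 18.1% | 33.0% |

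Adding the look-back month to the follow-up rows changes little: at r = 0.10, t = 13/12 gives 10.3% and t = 25/12 gives 18.8%.

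A discrete check agrees. At an assumed 1% per month, the look-back gives 1%, and look-back plus 12 months gives 1 − 0.99^13 = 12.2%. With n = 300 the 95% CI around 12.2% is 8.5% to 15.9%, which excludes 1%.

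**Laboratory tests.** Assume independent testing with probability q at each of four visits (Weeks 0, 12, 24 and 52). The chance of at least one test is 1 − (1 − q)^4. For q = 20% this is 59.0%, and for q = 50% it is 93.8%. This shows how far the open clause could move the item if it were applied literally.

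**The case against.** Several counter-arguments carry weight.

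- **On-treatment tests are defined separately.** Section 8.3.2 and the follow-up part of Table 5 both list them. Table 5's baseline rows for ANC, ALC and haemoglobin carry no follow-up window. A reader might infer that a first test in year 3 will be scored as pre-treatment compliance. No section defines that numerator, so the documents support only that the 8.3.1 wording permits it.
- **Follow-up capture has a purpose.** Section 6 says VTE risk should be reassessed periodically on treatment, and objective b concerns use in patients with risk factors, not only initiation. Recording later surgery and admissions is therefore legitimate. What does not survive is placing them in a baseline item with no follow-up counterpart.
- **The high-risk subgroup.** A reader might infer that the error carries into the maintenance-dose analysis in Section 8.7. The protocol does not say which items define that subgroup, and the Section 6 list of VTE risk factors other than cardiovascular and malignancy factors names major surgery and immobilization but not hospitalization. The point is conditional: if these items are used, membership would depend on future events.
- **Magnitude.** The same formula at four years gives 33.0% and 55.1%, and it is tempting to quote these or a general 20-fold inflation. Section 8.2.4 ends follow-up at discontinuation, and patients enter consecutively over the 4-year period, so few could contribute four years. If active disease raises admissions in the month before starting, the ratio falls further.
- **The +1 month laboratory tolerance.** The index date is the first identification of exposure in the registry, so some tolerance is defensible. Removing it would be partly a preference.

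**Conclusion.** The definition is wrong as written for three baseline items, not for baseline variables in general. It contradicts the opening rule of Section 8.3.1, and Table 5 repeats the contradiction for surgery and hospitalization.

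The direction needs no assumption: a window open to follow-up can only add positives, and adds more the longer patients are observed. The size does rest on assumptions. At 0.10 to 0.20 hospitalizations per patient-year, 0.8 to 1.7% becomes about 10 to 18% over one full year or 18 to 33% over two; the real figure depends on event rates and time on treatment. The consequence is firmest for surgery and hospitalization, which have no separate follow-up entry. For laboratory tests the fault is a duplicated clause that blurs the distinction between testing before and during treatment. The documents do not establish that reported pre-treatment compliance will be overstated.

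**What to change.** 1. In Section 8.3.1, delete the clause extending to follow-up from the laboratory, surgery and hospitalization items. Delete it from the surgery and hospitalization rows of Table 5 as well.
2. Limit baseline surgery and hospitalization to the one month before the index date.
3. Keep later laboratory tests only in Section 8.3.2. If the ±1 month tolerance stays, report tests on or before the index date separately from those in the month after it.
4. Add post-index surgery and hospitalization to Section 8.3.2 and to the follow-up part of Table 5 as dated variables.
5. In ICC, mark pre-index hospitalization as not assessable unless it is recorded at Week 0.

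The cost is wording and smaller baseline percentages, with possibly one item not assessable in ICC. No new data are needed: Table 5 already plans dates for surgery, hospitalization and most laboratory measurements, subject to availability in each registry.

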## 8.3.2. Follow-up Variables

Follow-up variables assessed during filgotinib treatment will include (as per availability by each registry):

- Filgotinib maintenance dose and average daily dose
- Diagnosis of TB
  - Date of diagnosis
- Serious acute infection
  - Date of diagnosis
- Diagnosis of viral hepatitis
  - Date of diagnosis
- Diagnosis of herpes zoster
  - Date of diagnosis
- Pregnancy
  - Start of pregnancy
- Use of live-attenuated vaccines
- Laboratory monitoring of lipids (total cholesterol, high- and low-density lipoproteins [HDL, LDL], triglycerides) around 12 weeks after initiation of filgotinib treatment and thereafter
- Laboratory measurements (any time during follow-up)
  - ANC
  - ALC
  - Hb
- VTE event
  - Date of VTE diagnosis

## 8.3.3. Exposure Definition

## 8.3.3.1. ENEIDA (ES)

Exposure to the drugs of interest is recorded in specific predefined fields and includes items such as the specific drug, its dose, and the dates of start and end of prescription. The definition of exposure assumes that if the drug is recorded in ENEIDA, it is being used by the patient as instructed (a common assumption in observational drug utilization research).

#### 8.3.3.2. ICC (NL)

In ICC exposure to the drugs of interest is recorded in specific predefined fields and includes items such as the specific drug, its dose, and the date of start of prescription. In the case the patient stops the drug, this will be recorded as well. The definition of exposure assumes that between the start and the stop date the drug is being used by the patient as instructed.

#### 8.3.3.3. SWIBREG (SWE)

Drug exposures for a small molecule such as filgotinib is captured in the Prescribed Drug Register ([PDR] i.e. all dispensed prescriptions of the drug). A dispensing will be assumed to last for 180 days, after which a lack of a new dispensed prescription will be counted as a treatment hiatus.

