Filgotinib (Jyseleca®) is an oral, adenosine triphosphate-competitive, reversible Janus kinase (JAK) 1 preferential inhibitor. JAKs are intracellular enzymes that transmit signals arising from cytokine or growth factor-receptor interactions on the cellular membrane to influence cellular processes of hematopoiesis, cytokine signaling, and immune cell function. Within the signaling pathway, JAKs phosphorylate and activate signal transducers and activators of transcription (STATs) that modulate intracellular activity including gene expression. Filgotinib modulates the signaling pathway by attenuating the phosphorylation and activation of STATs (Dhillon & Keam, 2020). In addition to their use in rheumatoid arthritis (Harrington et al., 2020), JAKi's have also been studied in IBD including UC (Feagan et al., 2021; Harris & Cummings, 2021; Mannucci et al., 2022; Taneja et al., 2021).

Jyseleca was initially approved in the European Union (EU) for moderately to severely active rheumatoid arthritis in September 2020. In November 2021 Jyseleca additionally received EU approval as induction and maintenance therapy in adult patients with moderately to severely active UC who have had an inadequate response with, lost response to, or were intolerant to either conventional therapy or a biologic agent. This was based on data from the pivotal Phase 2b/3 SELECTION program which provided information on filgotinib's efficacy and safety (D'Amico et al., 2022). Assessment of safety using only data from randomized clinical trials (RCTs) however, is subject to limitations, like the relatively small sample sizes, more restrictive

inclusion and exclusion criteria, and relatively short duration of follow-up. Long-term safety data are therefore needed in patients treated with filgotinib in real-world clinical settings and in patient populations where there are limited RCT data. For this reason, a non-interventional post-authorization safety study (PASS) assessing the long-term safety of filgotinib is being conducted using information from 3 European IBD registries (study ID: GLPG0634-CL-413).

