*MACE* (i.e. fatal and nonfatal CVD events; CVD comprises coronary heart disease [angina, myocardial infarction], congestive heart failure, cerebrovascular disease and peripheral artery disease]): In patients 65 years of age and older, patients who are current or past long-time smokers, and patients with history of atherosclerotic CVD or other CV risk factors, filgotinib should only be used if no suitable treatment alternatives are available.

*VTE* (includes deep venous thrombosis) and pulmonary embolism [PE]): In patients with CV or malignancy risk factors filgotinib should only be used if no suitable treatment alternatives are available.

In patients with known VTE risk factors other than CV or malignancy risk factors, filgotinib should be used with caution. VTE risk factors other than CV or malignancy risk factors include previous VTE, patients undergoing major surgery, immobilization, use of combined hormonal

contraceptives or hormone replacement therapy, inherited coagulation disorder. Patients should be re-evaluated periodically during filgotinib treatment to assess for changes in VTE risk.

Patients with signs and symptoms of VTE should promptly be evaluated and filgotinib be discontinued in patients with suspected VTE, regardless of dose.

This longitudinal drug utilization study (DUS) is being conducted by the MAH as a Category 3 commitment to the EMA and to the Medicines and Healthcare products Regulatory Agency (MHRA) based on real-word secondary data derived from the same 3 IBD registries used for the filgotinib LTS PASS (GLPG0634-CL-413), namely the Estudio Nacional en Enfermedad Inflamatoria Intestinal sobre Determinantes Genéticos y Ambientales (ENEIDA) Register from Spain, the Initiative on Crohn and Colitis (ICC) Register from the Netherlands, and the Swedish National Quality Registry for Inflammatory Bowel Disease (SWIBREG).

This protocol follows the approach used in the already endorsed DUS for filgotinib in RA (GLPG0634-CL-408), thereby also taking into account prior comments from the PRAC Rapporteur.

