#### 8.2.2. Inclusion Criteria

Across all 3 registries, adult patients ( $\geq$ 18 years) of any sex with UC that are enrolled in 1 of the 3 IBD registries after 10 March 2023 and during the observational period (complying with the register's requirements for inclusion including patient consent) and initiated on filgotinib after 10 March 2023. Initiation is defined as either no prior filgotinib use or prior use that was discontinued before 10 March 2023 (thus, patients who are non-naïve to filgotinib can be included).

There are no restrictions on patient inclusion in terms of either historical data or minimum amount of follow-up.

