## 8.2.4. Index Date, Follow-up

The index date (= start of follow-up) in each registry will be the date a patient starts UC treatment with filgotinib (i.e. the date of first identification of filgotinib exposure in the registry) after the EC decision date. The patient's total follow-up time is defined as the time from the filgotinib index date until the earliest of treatment discontinuation, study withdrawal (withdrawn from the registry, death or loss to follow-up) or end of study.

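### No rule ties a filgotinib start to UC, so in Sweden, where exposure is any dispensing, a UC patient given the drug for rheumatoid arthritis can enter and be assessed as UC prescribing

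*Protocol*

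**What the plan says.** Section 8.2.4 says the index date "will be the date a patient starts UC treatment with filgotinib". In brackets it then gives the working rule: "the date of first identification of filgotinib exposure in the registry". The first phrase carries an indication; the second does not.

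Section 8.2.2 requires an adult with UC, enrolled in a registry, "and initiated on filgotinib after 10 March 2023". It does not say that the start must be for UC. The only exclusion (Section 8.2.3) is continuing use from before the decision date.

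For Sweden, Section 8.3.3.3 states: "Drug exposures for a small molecule such as filgotinib is captured in the Prescribed Drug Register". It explains this as every dispensed prescription of the drug. Section 8.6.3 describes the linked Swedish dataset as covering all patients with UC.

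Section 6 notes a second licence: "Jyseleca was initially approved in the European Union (EU) for moderately to severely active rheumatoid arthritis in September 2020". It also refers to an "already endorsed DUS for filgotinib in RA (GLPG0634-CL-408").

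The indication block of Table 5 lists UC severity and its date, the filgotinib start date and age at that date. It has no variable for the reason filgotinib was prescribed. The limitations in Section 8.9 do not raise the matter.

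**The concern.** The intended index event is a UC treatment start; the event that would be programmed from the text is any filgotinib start in a person with UC. The two differ for a patient who has both UC and RA and receives the drug for RA.

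Such a patient would be measured against three UC-specific yardsticks: the UC posology in Section 6, the UC indication and severity, and the history of UC treatment. The last matters because Section 8.9 relies on prior UC treatment as a partial stand-in for the unmeasurable question of whether suitable alternatives existed. A patient treated for RA may have little or no advanced UC therapy behind them and would distort that description.

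Sweden is the most exposed registry because its source covers every dispensing, whoever prescribed. ICC enrols patients starting novel drugs for IBD (Section 8.4.2), and ENEIDA data come from gastroenterology practices (Section 8.4.1.1). The missing words in Sections 8.2.2 and 8.2.4 nevertheless apply to all three.

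**Working it through.** **Does any text restore the indication?**

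| Place | Content | Ties the start to UC? |
|---|---|---|
| 8.2.4, first phrase | start of UC treatment | yes, as intent |
| 8.2.4, working rule | first exposure identified | no |
| 8.2.2 | UC diagnosis plus filgotinib start | no |
| 8.2.3 | prevalent users only | no |
| 8.3.3.3 | all dispensings | no |
| Table 5, indication block | severity, dates, age | no |
| 8.9 | limitations | not mentioned |

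Only a statement of intent does so, and the working rule beside it drops the condition.

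**The plan's own precision figure.** Section 8.5 takes p = 10% and n = 300. SE = √(0.10 × 0.90 / 300) = 1.73 points; 95% CI = 10 ± 1.96 × 1.73 = 6.6% to 13.4%. This reproduces the stated 1.7% and 6.6% to 13.4%, and is not in dispute.

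**Shift in an overall proportion.** Let f be the share of starts that are for RA, and pUC and pRA the proportions with some characteristic among UC and RA starts. The observed proportion moves by f × (pRA − pUC). The documents give none of these. Assume pUC = 10%, pRA = 30% or 50%, and f from 0.5% to 10%:

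| f | Patients of 500 | Shift, pRA 30% | in SEs (n = 300) | Shift, pRA 50% | in SEs (n = 300) |
|---|---|---|---|---|---|
| 0.5% | 2.5 | 0.1 | 0.06 | 0.2 | 0.12 |
| 1% | 5 | 0.2 | 0.12 | 0.4 | 0.23 |
| 2% | 10 | 0.4 | 0.23 | 0.8 | 0.46 |
| 5% | 25 | 1.0 | 0.58 | 2.0 | 1.15 |
| 10% | 50 | 2.0 | 1.15 | 4.0 | 2.31 |

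Shifts are in percentage points.

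**Make-up of a subgroup.** Take patients aged 65 and over as the example. Section 6 gives a separate UC posology for them, and Section 8.7 plans a maintenance-dose assessment in high-risk patients. With 10% of UC starters and q = 30-40% of RA starters in that group (assumed), the RA share of the subgroup is f·q / [(1 − f) × 0.10 + f·q]:

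- f = 1%: 0.003/0.102 to 0.004/0.103 = 2.9-3.9%
- f = 2%: 0.006/0.104 to 0.008/0.106 = 5.8-7.5%
- f = 5%: 0.015/0.110 to 0.020/0.115 = 13.6-17.4%

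At f = 5% the subgroup itself grows only from 10% to 11.0-11.5% of starters.

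**Likely Swedish numbers.** Section 8.9 reports 44 Swedish users between 12 November 2021 and 10 March 2023, about 16 months. If that rate held (an assumption; uptake may change), 48 months would give 44 / 16 × 48 = 132 patients and an SE at 10% of √(0.09 / 132) = 2.6 points. At f = 2% that is 132 × 0.02 = 2.6 RA starts, about one of them in a 65-and-over group of about 14.

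**The case against.** The strongest reply is that Section 8.2.4 already says UC treatment, so the rest is a wording gap, and that Section 8.7 sends detailed methods to a SAP not shown here. The second part stands for programming detail: how registry and dispensing records are combined may properly be left to the SAP. It does not cover eligibility and the index date, which the protocol itself fixes without the condition.

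Several stronger readings are tempting but unsupported:

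- *The Prescribed Drug Register holds no indication.* Sections 8.3.3.3 and 8.4.3.2 mention no such field; they do not say it is absent.
- *The Swedish index date certainly comes from dispensings.* This is inferred from Sections 8.2.4 and 8.3.3.3 together. Table 5 names no Swedish source for the start date. Section 8.4.3.1 calls SWIBREG the main source and gives the drug register a confirming role, and Table 5 takes discontinuation from both.
- *The problem is confined to Sweden.* The ENEIDA and ICC descriptions make it less likely there, but do not rule it out.
- *RA-indicated starts in older or high-risk patients would be counted as breaches of restrictions not meant for them.* Section 6 describes the age, cardiovascular and malignancy restrictions without limiting them to UC, and the communication to prescribers likewise. Section 8.9 concedes that availability of alternatives cannot be reliably assessed, so these groups are described, not scored as violations.

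It is also fair that the frequency is unknown and the effect on overall proportions small at low contamination.

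**Conclusion.** The point holds as a gap between intent and rule. As written, a SWIBREG patient with UC who is dispensed filgotinib for RA can be included and assessed on UC posology, UC indication and severity, and prior UC treatment. The text permits this; it does not show that it happens or how often.

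Every size above rests on assumed values for the RA share and for how RA starters differ. At 1-2% of starts, the shift in an overall proportion is 0.2-0.8 points, or 0.12-0.46 of the standard error at 300 patients. It exceeds one standard error only with several percent of RA starts and a marked difference between the groups. The practical relevance lies in small subgroups, where one or two such patients are a visible share. This merits a short protocol correction; it does not threaten the study as a whole.

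**What to change.** 1. In Section 8.2.2, require for all three registries that filgotinib was initiated for UC, and align the bracketed rule in Section 8.2.4 with it.
2. In Section 8.3.3.3, flag Swedish dispensing-based starters who have an RA diagnosis in the National Patient Register. That register is already linked, is ICD-coded and covers specialist outpatient visits (Section 8.4.3.2). Report how many are flagged.
3. Treat any SWIBREG filgotinib record as supporting evidence of UC use, not as an entry requirement. Its completeness for filgotinib starts is not documented: the remark in Table 5 about good coverage for targeted therapies belongs to reasons for switching, and Section 8.2.1.3 describes registry coverage as patchy. Making it mandatory could remove true UC starts.
4. Show the posology, indication and prior-treatment results with and without flagged patients who lack evidence of UC use.

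The cost is one eligibility phrase, one derivation from registers already in use, and one sensitivity row. Some patients with both diseases who were truly treated for UC may be flagged, which is why both sets of results should be shown.
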